4.2.2. Laboratory test

Laboratory data including hematology, urinalysis, stool routine, blood biochemistry, coagulation function, and thyroid function (T3, FT3, FT4, TSH) will be collected at the visit time points specified in the protocol.

4.2.3. Vital signs

Vital signs including body temperature, pulse, respiration, diastolic blood pressure, and systolic blood pressure will be collected at the protocol-preset time points.

4.2.4. 12-Lead ECG

Heart rate, PR, QT, QTc, and QRS data will be collected at the protocol-preset time points.

4.2.5. Physical examination

Physical examinations include general condition, head and face, skin system, lymph nodes, eyes, ears, nose and throat, oral cavity, respiratory system, cardiovascular system, abdomen, reproductive-urinary system, musculoskeletal system, nervous system, and mental state. These data will be collected at protocol-specified visit/time points.

4.2.6. Other safety endpoints

Echocardiography, etc.

5. STATISTICAL ANALYSIS

All efficacy and safety analyses will be based on the following populations/groups:

- **Driver gene negative population:** Subjects who are negative or not tested for EGFR and also negative or not tested for ALK fusion gene are classified into negative population. Including:
 - (1) Apatinib 250 mg + SHR1210 200 mg (Stage I): subjects who are negative or not tested for EGFR and also negative or not tested for ALK fusion gene;
 - (2) Cohort 1;
 - (3) Cohort 3;

Apatinib 250 mg + SHR1210 200 mg are used in both Cohorts 1 and 3 in Stage II.

- **Driver gene positive population:** Subjects who are positive for EGFR or ALK fusion gene are classified into positive population. Including:
 - Subjects who use apatinib 250 mg + SHR1210 200 mg and are positive for EGFR or ALK fusion gene in Stage I;
 - Cohort 2: Apatinib 250 mg + SHR1210 200 mg are used in Cohort 2.
- **Cohort 4:** Apatinib 250 mg + SHR1210 200 mg are used in Cohort 4.
- **Apatinib 375 mg + SHR1210 200 mg:** Only subjects who receive apatinib 375 mg + SHR1210 200 mg in Stage I are included.

5.1. General Considerations

5.1.1. Analysis sets

Full analysis set (FAS)

All enrolled subjects who have received at least one dose of the study drug are included.

Evaluable analysis set (ES)

ES is a subset of FAS, which is defined as the subjects who have received at least one dose of the study drug, and have at least one post-baseline imaging response evaluation. If there is a new anti-tumor treatment, there should be a post-baseline tumor imaging response evaluation no later than the start date of the new anti-tumor treatment.

Per-protocol set (PPS)

All enrolled subjects who have received at least one dose of the study drug without major protocol deviation.

Safety set (SS)

All enrolled subjects who have received at least one dose of the study drug.

DLT analysis set

Subjects enrolled in Stage I who have developed DLT during the tolerability observation period (four weeks) or have completed the tolerability observation period. Subjects with SHR-1210 dose < 90% of the prescribed dose due to non-clinically significant toxicity (such as injection reaction) during the tolerability observation period are not included in the DLT analysis set.

Table 1. Analysis sets and corresponding endpoints

Endpoint	Analysis Sets				
	FAS	ES	PPS	SS	DLT Analysis Set
BOR (%)	X	X	X		
ORR (%)	X	X	X		
CBR (%)	X	X	X		
TTR (months)	X				
PFS (months)	X				
DoR (months)	X				
12-Month Overall Survival Rate (%)	X				
OS (months)	X				
Safety (AE, LAB, VS, ECG, and PE)				X	
DLT Events					X

5.1.2. General rule and analysis

Baseline

Unless otherwise stated, the "baseline" in this study is defined as the last non-missing measurement value obtained prior to the first dose of study drug, including 1) visits during screening period before the first dose of study drug; 2) measurements taken on the day of and prior to the first dose (do not serve as baseline value if time is not distinguishable). In the event of repeated measurements on the same day which cannot be distinguished by time, the mean value of a continuous variable will serve as baseline value, or the lower-severity grade of a categorical variable will serve as baseline value.

Study days

The day of the first dose is used as the start date of the study (Day 1).

- If the evaluation date (adverse event, laboratory tests, etc.) is on or after the study medication, the study days shall be calculated as follows: Study days = evaluation/event date – start date of study + 1.
- If the evaluation date (baseline characteristics, medical history, etc.) is before the study medication, the study days shall be a negative figure and shall be calculated as follows:
Study days = evaluation/event date – start date of study;

General analysis

Unless otherwise specified, the following descriptive statistics will be summarized by the type of variables:

- The continuous variables will be summarized using mean, standard deviation, median, maximum, minimum, and quartile.
- The categorical variables will be summarized using frequency and percentage;
- For time-to-event data, Kaplan-Meier method will be used to estimate the survival function and median time to event onset, and a survival curve will be plotted.

Number of decimal places

Unless otherwise specified, number of decimal places in the analysis report will be determined as per the following rules:

- The decimal places of the minimum and maximum will remain the same as those of the raw data to be acquired. Mean and median should have one more decimal place than those of the raw data, and the standard deviation should have 2 more decimal places than that of the raw data. However, there can only be at most 4 decimal places.
- The percentage will be rounded to 1 decimal place. If the frequency is 0, the percentage is not displayed.
- The *P* value will retain four decimal places. If the *P* value is < 0.0001, it will be expressed as "< 0.0001". If the *P* value is > 0.9999, it will be reported as "> 0.9999".
- The 95% CI, if being a decimal, will retain at least 2 decimal places, up to 4 decimal places. Details are as follows: The 95% confidence interval will have one more decimal place than that of the raw data. If the raw data have no decimal place, the 95% confidence interval will retain 2 decimal places; if the raw data have 4 or more decimal places, the 95% confidence interval will retain at most 4 decimal places.
- Time to event (months) will be rounded to one decimal place.

Analysis software

All statistical analyses will be conducted using SAS® 9.4.

5.1.3. Derived variables

Table 2. Derived variables of apatinib

Variable	Apatinib
Protocol-Specified Method of Administration	Administered once daily in 4-week cycles. Subjects who receive apatinib 375 mg + SHR1210 200 mg in Stage I: 375 mg per dose; others: 250 mg per dose
Duration of Drug Exposure (months)	$(\text{Date of last dose} - \text{date of first dose} + 1) / 30.4375$
Planned Duration of Treatment (months)	$(\text{Date of last dose} - \text{date of first dose} + 1) / 30.4375$
Actual Cumulative Dose of All Cycles (mg)	Summarize the actual dose in all cycles (mg): $[\text{duration of drug exposure (months)} \times 30.4375 \text{ (days/month)} - (\text{end date of dose modification} - \text{start date of dose modification} + 1) \text{ (days)}] \times \text{first dose} + (\text{end date of dose modification} - \text{start date of dose modification} + 1) \text{ (days)} \times \text{dose after modification (mg/day)} - (\text{end date of dose interruption} - \text{start date of drug interruption} + 1) \text{ (days)} \times \text{interrupted dose (mg/day)}$
Planned Dose Intensity (mg/day)	Subjects who receive apatinib 375 mg + SHR1210 200 mg in Stage I: 375 (mg/day); others: 250 (mg/day)
Actual Dose Intensity (mg/day)	$\text{Actual cumulative dose of all cycles (mg)} / [\text{planned duration of treatment (days)}]$
Relative Dose Intensity (%)	$100 \times [\text{actual dose intensity (mg/day)}] / [\text{planned dose intensity (mg/day)}]$

Table 3. Derived variables of SHR-1210

Variable	SHR-1210
Protocol-Specified Method of Administration	Administered once every 14 days, 200 mg each time, in 4-week cycles
Duration of Drug Exposure (months)	$(\text{Date of last dose} - \text{date of first dose} + 14) / 30.4375$
Planned Duration of Treatment (months)	$(\text{Date of last dose} - \text{date of first dose} + 14) / 30.4375$
Actual Cumulative Doses of All Cycles (doses)	Total number of SHR-1210 doses actually received by the subject
Planned Dose Frequency Intensity (doses/2 weeks)	1
Actual Dose Frequency Intensity (times/2 weeks)	$(\text{Actual cumulative doses of all cycles} / [\text{planned duration of treatment (months)} \times 30.4375 / 7 \text{ (weeks/month)} / 2])$
Relative Dose Frequency Intensity (%)	$100 \times [\text{actual dose frequency intensity (doses/2 weeks)}] / [\text{planned dose frequency intensity (doses/2 weeks)}]$

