6.3 Administration Regimen

SHR-1210 will be administered via intravenous drip (without prophylaxis) with a fixed dose of 200 mg within 30 min (not less than 20 min, no more than 60 min), once every 2 weeks. Each cycle contains 4 weeks (the subjects for the expanded PK study will receive one dose on D1 of Cycle 1 of the study) and the longest period of drug use is 2 years.

Apatinib will be orally administered after meals (the subjects for the expanded PK study will receive the drug orally under fasting on Day 28 of Cycle 1 and Day 28 of Cycle 2), once a day, and one tablet (250 mg/tablet or 375mg/tablet) or 2 tablets (250 mg/tablet, 500 mg dose group) each time. The drug administration will be continued through the study.

Subjects enrolled for the study in the tolerability observation stage and subjects enrolled for the Stage II of the study will be given SHR-1210 on D1 and D15 of each cycle from the beginning of treatment; apatinib will be given via oral administration once daily.

Subjects enrolled for the expanded PK study will be given SHR-1210 on D1 in Cycle 1 and on D1 and D15 in each cycle starting from Cycle 2. These subjects will also be given daily oral administration of apatinib continuously starting from D22 in Cycle 1.

Definition of postprandial administration: administration within 30 min after the end of a meal.

The subjects will continue to use the study drugs until the criteria for treatment discontinuation specified in the protocol are met.

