2.1. Study Design

Study design of Stage I:

A multi-arm, multi-center, open-label clinical study

Patients with advanced NSCLC who have failed standard treatment will be enrolled.

Three dose groups, i.e., apatinib 250 mg, oral, q.d. + SHR-1210 200 mg, IV, q2W, apatinib 375 mg, oral, q.d. + SHR-1210 200 mg, IV, q2W, and apatinib 500 mg, oral, q.d. + SHR-1210 200 mg, IV, q2W, are set to explore the tolerability of the combination therapy.

Ten to twelve subjects will be enrolled in each dose group (to make sure that at least 10 subjects will complete the tolerability evaluation), and the first cycle (28 days) of continuous treatment will be used as the observation period for tolerability. A dose will be considered tolerable if the proportion of subjects with clinically significant toxicity is < 0.33 .

After completing the tolerability observation period, subjects will continue the treatment until occurrence of any event that meets the criteria for discontinuation.

After completing the tolerability observation period, the study will enter Stage II for further observation of efficacy and safety.

After completing the tolerability observation period, 10 to 12 subjects will be enrolled in each dose group for an expanded pharmacokinetic (PK) study. In cycle 1 of the expanded PK study, one dose of SHR-1210 will be administered on D1 followed by PK blood sampling. Then, apatinib will be started on D22 after the completion of PK blood sampling, while another PK blood sampling will be carried out on D28. Starting from D1 of cycle 2, SHR-1210 will be administered once every 14 days, while apatinib will be administered orally every day. PK blood sampling will be carried out on D1 of cycle 2 after the administration of SHR-1210 and on D28 after the administration of apatinib. After the blood sampling is completed, subjects will continue the treatment until occurrence of any event that meets the criteria for discontinuation.

Design of Stage II:

A single-arm/double-arm, multi-center, open-label clinical study

According to the tolerable doses for combination therapy determined in Stage I, apatinib 250 mg, q.d. oral + SHR-1210 200 mg, IV, q2W are selected, and patients with advanced NSCLC who have failed first-line chemotherapy or patients with non-squamous non-small cell lung cancer with a high tumor mutation burden (TMB) confirmed by the central laboratory will be enrolled. According to the molecular and pathological classifications, the subjects are divided into:

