5.4.1. Extent of exposure

Extent of exposure is defined in Section 5.1.3. The specific definitions of the derived variables of apatinib and SHR1210 are shown in [Table 2](#) and [Table 3](#).

The actual cumulative dose of all cycles, duration of drug exposure, actual dose intensity, relative dose intensity, etc. of apatinib, and the actual cumulative doses of all cycles, duration of drug exposure, actual dose frequency intensity, and relative dose frequency intensity of SHR1210 will all be described using mean, standard deviation, maximum, minimum, and median. The use of study drugs SHR-1210 and apatinib in the treatment period will be summarized by descriptive statistics. For the relative dose frequency intensity of SHR-1210, the relative dose intensity values of apatinib are summarized in two categories: $<$ or $\geq 80\%$.

The dose interruption and dose modification of apatinib and the dose interruption of SHR1210 during the study will be summarized.

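### SAP Table 3 counts a planned SHR-1210 dose every 14 days from first dose, so PK-expansion subjects with two or more doses can never reach 100% relative dose frequency, even when fully compliant

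*SAP*

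**What the plan says.** SAP 5.1.3, Table 3, describes the protocol-specified SHR-1210 administration as "Administered once every 14 days, 200 mg each time, in 4-week cycles". Its other rows are:

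- Exposure duration and planned treatment duration are both last dose date minus first dose date plus 14 days, converted to months.
- The numerator is "Total number of SHR-1210 doses actually received by the subject".
- Planned dose frequency intensity is the constant 1 dose per 2 weeks.
- Relative dose frequency intensity is actual frequency over planned frequency, in percent.

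Table 3 makes no exception for any subject. Table 2, for apatinib, does branch by dose group.

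Protocol 6.3 gives a separate schedule for the PK expansion: "Subjects enrolled for the expanded PK study will be given SHR-1210 on D1 in Cycle 1 and on D1 and D15 in each cycle" from Cycle 2 onward. SAP 2.1 agrees: "In cycle 1 of the expanded PK study, one dose of SHR-1210 will be administered on D1 followed by PK blood sampling", with 14-day dosing starting on D1 of Cycle 2. All other subjects receive SHR-1210 on D1 and D15 of every cycle from the start.

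SAP 5.4 bases safety analyses on the safety set, which includes the PK-expansion subjects. SAP 5.4.1 has a sentence that opens with SHR-1210 relative dose frequency intensity and continues "the relative dose intensity values of apatinib are summarized in two categories", split at 80%.

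**The concern.** Relative dose intensity is meant to show how much of the planned treatment was delivered. It does so only if the denominator is the subject's own plan. For PK-expansion subjects Table 3 counts a Day 15 dose in Cycle 1 that the protocol never schedules.

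The ratio then cannot tell a subject who followed the design from one who had a dose skipped, for instance for toxicity under Protocol 6.4. The distortion is uneven across reporting groups. Cohort 4 has no PK-expansion subjects, the pooled 250 mg populations have few, and the 375 mg group may have many. A lower figure in the 375 mg group could be misread as poorer delivery of SHR-1210 alongside the higher apatinib dose.

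**Working it through.** **Inputs.** Table 3 formula and constant: SAP 5.1.3. PK-expansion schedule: Protocol 6.3 and SAP 2.1, giving doses on days 1, 29, 43, 57 and so on. Regular schedule: days 1, 15, 29 and so on. PK-expansion size of 10–12 per dose group and planned cohort sizes of 78, 38, 38 and 20: SAP 2.3. Reporting populations: SAP 5.

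**Formula.** The months conversion (30.4375) cancels, and the planned frequency is 1, so

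relative intensity = 100 × doses / [(last − first + 14)/14].

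**Regular schedule first.** With k doses 14 days apart, last − first = 14(k − 1). The denominator is k and the result is 100% at every dose count. The formula does what it should for these subjects.

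**PK expansion, fully compliant.** For k of 2 or more, last − first = 28 + 14(k − 2) = 14k. The denominator is (14k + 14)/14 = k + 1, so the score is k/(k + 1).

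| Last dose | Doses | Denominator | Score |
|---|---|---|---|
| C1D1 | 1 | 1 | 100% |
| C2D1 | 2 | 3 | 66.7% |
| C2D15 | 3 | 4 | 75.0% |
| C3D1 | 4 | 5 | 80.0% |
| C3D15 | 5 | 6 | 83.3% |
| C4D1 | 6 | 7 | 85.7% |
| C6D15 | 11 | 12 | 91.7% |
| C13D15 | 25 | 26 | 96.2% |
| C26D15 | 51 | 52 | 98.1% |

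The excess in the denominator is always one 14-day interval, so the score equals that of a regular-schedule subject with one missed dose.

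**The 80% split, if it covers SHR-1210.** Compliant subjects whose last dose is C2D1 or C2D15 fall below 80%. At C3D1 the score is exactly 80.0%. A C3D1 dose given 1 day late, inside the ±3-day window, gives 4/(71/14) = 78.9%; 3 days late gives 4/(73/14) = 76.7%.

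**Effect on group means.** Assume 12 PK subjects, each with 3 doses (a 25-point shortfall), all in one population with no other Stage I subject, full planned Stage II enrolment, and everyone else at 100%.

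- Driver-gene-negative (Cohorts 1 and 3): 12 × 25 / (78 + 38 + 12) = 300/128 = 2.3 points.
- Driver-gene-positive (Cohort 2): 12 × 25 / (38 + 12) = 300/50 = 6.0 points.
- 375 mg group, if it had a PK expansion: with equal numbers of PK and tolerability subjects, 25/2 = 12.5 points. Varying each part over 10–12 gives 10/22 × 25 = 11.4 to 12/22 × 25 = 13.6 points.

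**The case against.** The case for leaving Table 3 alone is mainly about size, and much of it stands.

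- **Group structure.** A reader might infer that PK subjects are half of each Stage I dose group, so that group means drop from 100% to 87.5% throughout. The documents do not support that. SAP 5 splits the Stage I 250 mg subjects by driver-gene status and pools them with Stage II cohorts. Only the 375 mg group is reported alone, and the SAP lists no 500 mg group. Protocol 3.1 opens PK expansion in a dose group only once that dose is confirmed tolerable, and the documents do not show that it took place at 375 mg. Three full groups of 20–24 would also need 60–72 subjects, against the 40–60 stated for Stage I.
- **Early stopping.** The 3-dose scenario has every PK subject stop at C2D15. The shortfall shrinks with time on treatment: at 10 doses it is 100 − 10/11 × 100 = 9.1 points. A subject who stops after C1D1 scores 100%.
- **The 80% class.** It is tempting to say outright that compliant subjects will be tabulated below 80%. The SAP 5.4.1 sentence is garbled and, in its main clause, names only apatinib. Covering SHR-1210 is a plausible reading, not a stated rule.
- **Other exposure outputs.** Doses received, duration of exposure and dose interruptions are also reported, and none uses the planned-frequency constant. It would be too strong to say that the exposure tables as a whole misstate delivery.

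None of this rescues the ratio. The row claims to state the protocol's own schedule, so the constant cannot be read as a deliberate common reference, and no other section corrects it.

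**Conclusion.** The point holds as a derivation error. For PK-expansion subjects with at least two SHR-1210 doses, Table 3 reports full compliance as k/(k + 1). That result follows from the documents without further assumption. The 80% consequence depends on how SAP 5.4.1 is read.

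The group effects are conditional on 12 PK subjects at 3 doses each and planned enrolment: at most about 2.3 points (driver-gene-negative) or 6 points (driver-gene-positive). About 12 points is possible only at 375 mg and only if PK expansion took place there. Longer treatment makes all three smaller; stopping at 2 doses would make them larger, since the shortfall is then 33.3 rather than 25 points.

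The consequence is minor: one descriptive safety ratio. ORR, the survival endpoints and the sample size do not depend on it. Apatinib in Table 2 is unaffected provided that its first dose date means the first apatinib dose (Day 22 for these subjects), which is an assumption.

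**What to change.** In SAP Table 3, for PK-expansion subjects with a dose on or after C2D1, define

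planned doses = (last dose date − first dose date + 14)/14 − 1,

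and relative dose frequency intensity = 100 × doses received / planned doses. Leave the formula unchanged for a subject who received only C1D1.

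Full compliance then scores 100% at every dose count (2/2, 3/3, 4/4, 51/51). Real omissions still show: C1D1 followed only by C2D15 gives 56/14 − 1 = 3 planned and 2 received, or 66.7%.

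Use this form rather than restarting the clock at the actual C2D1 date, which would hide a delay of that dose. For example, with C2D1 given 3 days late as the last dose, the form above gives 2/(45/14 − 1) = 90.3%, while a restart gives 2/2 = 100%.

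The SAP 5.4.1 sentence should also say plainly whether the 80% split applies to both drugs.

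The cost is one line in Table 3, one program condition and one reworded sentence. SAP 2 says that the final draft will be completed before database lock, so the change belongs in that draft. It alters the derivation only and implies no change to dosing.

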5.1.4. Covariates and subgroups

Baseline characteristics may affect the efficacy, and the efficacy will be analyzed according to subgroup classification. Baseline characteristics include: gender (male/female); age (≥ 65 years or < 65 years); ECOG performance status (0/1); smoking history (yes/no); number of metastasis sites (≤ 2 or > 2); clinical stage (IIIb/IV); brain metastases (yes/no); liver metastases (yes/no); history of tumor surgery (yes/no); history of radiotherapy (yes/no); PD-L1 expression on tumor cells (TC) in tumor tissue ($\geq 1\%$ / $< 1\%$); KRAS mutation (positive/negative), etc.

5.1.5. Missing data

5.1.5.1. Medical history

For the missing dates of medical history (including the dates of first pathological diagnosis, progression/recurrence, and response prior to the first dose of the study drug), the rules for imputing are as follows:

- If the day is missing, it will be imputed with 1 of that month.
- If both month and day are missing and the year is prior to the year of the first administration, the date will be imputed with 1 Jan.
- If both month and day are missing and the year is the same as that of the first administration, the date will be imputed with 1 Jan.
- If the date is completely missing, it will not be imputed.

5.1.5.2. Adverse events

If the date related to an AE is missing, the rules for imputing are as follows:

- If the start date of an AE is completely missing, the date will be imputed with the date of the first administration.
- If only the day of the start date of the AE is missing with the same year and month as those of the first administration, the day will be imputed with that of the date of the first administration.
- If both the month and day of the start date of the AE are missing with the same year as that of the first administration, the month and day will be imputed with those of the date of the first administration.
- In other cases, if the month or day of the start date of the AE is missing, it will be imputed with 1.

- If only the day of the end date of the AE is missing, the date will be imputed with the last day of the month (before the date of death). If the last day of the month is later than the date of death, it will be imputed with the date of death.
- In other cases, if the end date of the AE is missing, the date will not be imputed.

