- [11] Hepatitis B, hepatitis C, and HIV tests: hepatitis B panel [If the test results are abnormal, viral replication (HBV DNA) test should be performed]; hepatitis C virus antibody (anti-HCV) test (If the test results are abnormal, virus titer should be tested); HIV antibody test.
- [12] Pregnancy test: The urine pregnancy test will be performed 72 h before the first dose for females of a childbearing age. If the result of the urine pregnancy test is positive, a serum pregnancy test shall be performed. If necessary, re-tests can be performed for confirmation.
- [13] If the subjects have previously been tested for EGFR mutations and ALK fusion gene, retests are not required; otherwise, the study site will perform relevant tests. If the subjects are positive for EGFR mutations, the test of ALK fusion gene will no longer be performed.
- [14] Adverse events: Adverse events will be collected from the time when the subjects sign the informed consent form. AEs unrelated to the study drugs will be collected to 30 days after the last dose. Treatment-related AEs will be collected until 90 days after the last dose of SHR-1210 or 30 days after the last dose of targeted anti-angiogenic therapy (whichever is longer). See the AE/SAE collection time limit in Section 8.3 for details.
- [15] Vital sign examination: Body temperature, respiration, pulse, blood pressure. The examination will be performed within 7 days before enrollment, on Day 1 and Day 15 of Cycle 1, Day 1 and Day 15 of subsequent cycles, upon completion of the study, and 30 days after treatment.
- [16] Physical examination and weight measurement: Examination of major body systems (head and face, skin system, lymph nodes, eyes, ears, nose, throat, oral cavity, respiratory system, cardiovascular system, abdomen, urogenital system, musculoskeletal system, nervous system and mental state) will be performed within 7 days before enrollment, on D1 and D15 of Cycle 1, D1 and D15 of subsequent cycles, upon completion of the study, and 30 days after the end of treatment. Body weight measurement will be started on D1 of Cycle 1 and performed on D1 of subsequent cycles, upon completion of the study, and 30 days after the end of treatment.
- [17] 12-Lead ECG: Performed within 7 days before enrollment, on Day 15 of Cycle 1, Day 1 and Day 15 of subsequent cycles, and upon completion of the study. Abnormalities in ECG must be confirmed twice via additional ECG tests.

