8.1.2 Criteria for severity assessment of adverse events

The severity of AEs will be determined using NCI-CTCAE v4.03. The following criteria can be used as references if an unlisted AE occurs:

Grade 1: mild; asymptomatic or mild symptoms; clinical or diagnostic observations only; treatment not indicated.

Grade 2: moderate; minimal, local, or non-invasive intervention indicated; limiting age-appropriate instrumental activities of daily living (e.g., cooking, shopping, using the telephone, counting money, etc.);

Grade 3: severe or medically significant but not immediately life-threatening; hospitalization or prolongation of hospitalization indicated; disabling; limiting self-care activities of daily living. Self-care ADL: Refer to bathing, dressing and undressing, feeding self, using the toilet, taking medications, and not bedridden.

Grade 4: life-threatening consequences; urgent intervention indicated.

Grade 5: death related to AE.

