5.4.3. Adverse events

AEs will be classified by treatment stage (before and after study treatment).

All AEs will be coded using MedDRA V24.0 and graded using NCI-CTCAE v4.03. Subject will be counted only once, even if the subject experiences more than one event within the same system organ class (SOC) and/or preferred term (PT). For the same AE reported in one subject multiple times but varying in CTCAE grade, the highest grade will be counted.

AEs will be ordered by descending incidence of SOC, and by descending incidence of PT within each SOC. If the incidence of ≥ 2 PTs is equal, the AEs will be ordered alphabetically. If there is no AE under a SOC or PT, the analysis will not be conducted.

Only TEAEs will be summarized. All AEs will be listed. AEs with completely missing onset time will be treated as TEAEs.

For AEs occurring after the start of study treatment, treatment-related AEs include those whose causality with the study drug is related, possibly related, or unassessable; if the causality assessment is missing, then the AE will be deemed treatment-related for analysis. AEs with any missing CTCAE grade will be analyzed based on the highest grade.

In AE summary table, AEs after study drug treatment will be analyzed according to the population/cohort, and the frequency and proportion will be used for statistical description. Analyses of AEs include but are not limited to the following:

- Any TEAE
- Treatment-related TEAE
- Any treatment-emergent serious adverse event (TESAE)
- Treatment-related TESAE
- CTCAE Grade ≥ 3 TEAE
- CTCAE Grade ≥ 3 treatment-related TEAEs
- Any TEAE with an incidence of $\geq 5\%$
- Treatment-related TEAE with an incidence of $\geq 5\%$
- AEs leading to treatment discontinuation
- Treatment-related AEs leading to treatment discontinuation
- AEs leading to discontinuation of SHR-1210
- Treatment-related AEs leading to discontinuation of SHR-1210
- AEs leading to discontinuation of apatinib
- Treatment-related AEs leading to discontinuation of apatinib
- AEs leading to interruption of SHR-1210
- Treatment-related AEs leading to interruption of SHR-1210
- AEs leading to interruption of apatinib
- Treatment-related AEs leading to interruption of apatinib
- AEs leading to dose reduction of apatinib
- Treatment-related AEs leading to dose reduction of apatinib
- AEs leading to death
- Treatment-related AEs leading to death
- TEAEs of special interest (SIEs, see Appendix 2 for specific classification)

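### The SAP's AE start-date imputation ignores the AE end date, so an event that ended before first dose can be tabulated as a TEAE; the missing-grade rule does not name a grade

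*SAP*

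**What the plan says.** SAP 5.1.5.2 sets an AE start date to the first-dose date in three situations.

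- Start completely missing: "If the start date of an AE is completely missing, the date will be imputed with the date of the first administration".
- Day missing, same month and year as first dose: "the day will be imputed with that of the date of the first administration".
- Month and day missing, same year as first dose: "the month and day will be imputed with those of the date of the first administration".

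For other partial dates, "In other cases, if the month or day of the start date of the AE is missing, it will be imputed with 1". The end-date bullets in the same section only complete the end date itself; they do not limit the start date.

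SAP 4.2.1 defines a TEAE by onset on or after the day of first treatment. SAP 5.4.3 adds, without exception, "AEs with completely missing onset time will be treated as TEAEs", and restricts the AE summaries to TEAEs. On collection, note 14 to the Protocol's Schedule of Activities says: "Adverse events will be collected from the time when the subjects sign the informed consent form". Protocol 7.1 allows 21 days of screening before first dose, and longer for Cohort 4 while TMB results are awaited.

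On severity, SAP 5.4.3 states: "AEs with any missing CTCAE grade will be analyzed based on the highest grade". It gives no number and does not separate fatal from non-fatal events. Protocol 8.1.2 defines the top of the scale: "Grade 5: death related to AE".

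**The concern.** A known end date before first dose settles the matter: the event was not treatment-emergent, however incomplete its start date. The SAP discards that information. It then produces a record that starts after it ends, and puts the event in the TEAE tables with a Day 1 onset under the time-to-first-onset formula in SAP 5.4.3.

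The SAP bounds its imputed dates elsewhere. An imputed start of new anti-tumor treatment cannot pass a known end date when the start is completely missing (5.1.5.4.3). An imputed AE end is limited by death (5.1.5.2), and an incomplete last-dose date falls back to the earlier of discontinuation and death (5.1.5.3). The AE start rule is the exception, which suggests an oversight.

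The missing-grade sentence is a second, separate defect, because two programmers could implement it differently. Missing causality is also counted as treatment-related in SAP 5.4.3, so the rules can compound on one incomplete record.

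Incidence and severity of AEs are the Stage I primary endpoint and a Stage II secondary endpoint (Protocol 2.2), so the tables affected are important ones.

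**Working it through.** The plan gives no figure to reproduce. The check applies the SAP 5.1.5.2 rules literally to hypothetical records, then classifies each under SAP 4.2.1. Assumed dates: first dose 20 March 2018, AE end 12 March 2018. Duration = end − imputed start + 1.

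| Recorded start | Imputed start | TEAE under SAP | Duration (days) | TEAE with end-date check |
|---|---|---|---|---|
| Completely missing | 20 March | Yes | 12 − 20 + 1 = −7 | No |
| Day unknown, March 2018 | 20 March | Yes | −7 | No |
| Day and month unknown, 2018 | 20 March | Yes | −7 | No |
| Day unknown, February 2018 | 1 February | No | 40 | No |
| 5 March 2018 | 5 March (complete) | No | 8 | No |

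The first three records are impossible and misclassified. The last two are already handled correctly, so the fault is confined to starts that are missing, or partial in the first-dose month or year, with an end before dosing.

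**Size per affected subject.** The change in a subject-level incidence is at most 100/n points. It is zero if the subject already has another event in that row. SAP 5.4 bases safety analyses on the safety set, and SAP 5 and 5.4.3 define the reporting groups. Using planned enrolment:

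- 375 mg group: 10–12 tolerability plus 10–12 PK subjects (Protocol 3.1) = 20–24. 100/24 = 4.2; 100/20 = 5.0 points.
- Cohort 4: 100/20 = 5.0 points, enough alone to bring a term into the tables of TEAEs with incidence of at least 5%.
- Driver-gene-negative population: Cohorts 1 and 3 give 78 + 38 = 116 before Stage I subjects are added. 100/116 = 0.86, so under 1 point.
- Driver-gene-positive population: Cohort 2 gives 38 before Stage I subjects are added. 100/38 = 2.6 points at most.

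**Missing grade.** Two readings are possible.

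- Top of the scale: an ungraded non-fatal AE is analysed as Grade 5, which Protocol 8.1.2 reserves for death.
- Highest recorded grade: SAP 5.4.3 uses the same phrase, a few lines earlier, for repeat reports of one AE in one subject. An ungraded repeat would then take that subject's recorded maximum, but an AE with only one, ungraded, record gets no grade.

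Neither reading gives a usable rule for a single ungraded non-fatal AE. No grade effect can be calculated, because the intended grade is not stated.

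**The case against.** Counting missing onset as treatment-emergent and missing causality as related is a usual conservative convention. The study is uncontrolled and descriptive, with no formal hypothesis (SAP 3), so the error runs against the drug. This stands, and the convention should remain wherever the end date is unknown or not clearly before first dose. It does not justify overriding a known pre-dose end date.

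The cases should also be few. Protocol 8.1.1 requires time of occurrence and severity to be recorded. Protocol 11.4.1 to 11.4.3 provide logic checks, repeated queries and complete monitoring of safety-endpoint data. All AEs are listed, so a start after an end would be visible. This limits the size of the problem, but imputation rules exist for records that stay incomplete after query.

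A reader might infer that every ungraded AE enters the Grade ≥ 3 rows. The documents do not support that: on the highest-recorded-grade reading it could be Grade 1 or 2, and the treatment-related row also depends on causality. A reader might also infer that false deaths would be reported. The grade-based rows named for the overall AE summaries use a Grade ≥ 3 threshold, so Grades 3, 4 and 5 count alike there, and AEs leading to death are a separate item. No named table would report a death that did not occur.

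**Conclusion.** The date rule is wrong as written in a narrow set of cases: an incomplete start of the three kinds above, combined with an end before first dose. The direction is to overstate harm. The size is the per-subject figures shown above, which assume planned enrolment and no other qualifying event in the row. The documents give no count of missing dates or grades, so the total effect is unknown and probably small. The missing-grade sentence needs correction on either reading.

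Two stronger conclusions are tempting but not supported. A reader might divide by the 10–12 tolerability subjects per dose group and get 8.3 to 10 points. The AE tables do not use that denominator: the 375 mg group also includes its PK subjects, and in the population summaries Stage I 250 mg subjects are pooled with the Stage II cohorts. A reader might also infer that the Stage I dose-tolerability decision is at risk. That decision rests on clinically significant toxicity in the 28-day observation period, analysed in a separate DLT set (Protocol 3.1; SAP 5.1.1 and 5.4.2), and the documents do not show that these imputations affect it.

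**What to change.** In SAP 5.1.5.2, add that an imputed AE start may not be later than the AE end date. Add also that an AE is not a TEAE if its end date is clearly before first dose, meaning that the latest date consistent with a complete or partial end date precedes it. Make the sentence in SAP 5.4.3 on completely missing onset subject to that exception; otherwise it would override the cap. Keep the conservative rule in all other cases.

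In SAP 5.4.3, replace the missing-grade sentence. After query, either analyse the AE at a stated non-fatal grade (for example Grade 3) or show it in a separate grade-missing row, and use Grade 5 only when the outcome is death.

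The cost is a few SAP sentences and one programming check for starts later than ends. No data collection changes. The SAP Introduction has the plan finalised before database lock, which is the natural time to make the change.
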